7.6 Third Manuscript

This paper will report results for household food insecurity presence and severity (secondary outcome), perceived income adequacy, and subjective social status (exploratory outcomes) at 6- and/or 12-months.

Household Food Insecurity

We will assess group differences in presence of household food insecurity as a binary outcome using mixed-effects logistic regression, and severity of household food insecurity as an ordinal outcome using mixed-effects logistic regression. Models will be adjusted for baseline severity of household food insecurity, and blocking variables (baseline A1C, gender, recruitment location). To improve the precision of effect estimates, models will also be adjusted for age, race/ethnicity, immigrant status, educational attainment, annual household income, home ownership, number of children living in the home, marital status, and diabetes duration. Additionally, all models will include baseline A1C data source (study measured vs administrative health data), and group (FoodRx vs comparison) indicator variables. We will include random intercepts for participants (participant study ID) to account for within-subject correlation due to repeated measures, and for primary care clinics (clinic study ID) to account for clustering of participants within clinics. Missing data for covariates will be addressed using full information maximum likelihood.

We will conduct subgroup analyses for household food insecurity by gender, recruitment location (urban setting, rural setting, Indigenous primary care clinic), Indigenous identity (self-identified as First Nations, Inuk, Métis), baseline A1C (6.5%-8.5%; 8.6%-12%).

We will conduct dose-response analyses to examine whether severity of household food insecurity differs based on the total value of incentives redeemed, a continuous variable, in the first 6 months for the mid-intervention analysis, and in the full 12-months for the post-intervention analysis.

In addition to per-protocol and as-treated analyses, we will conduct sensitivity analyses for household food insecurity to examine the impact on results when food insecurity is modelled as a continuous outcome using mixed-effects linear regression.¹²³

Perceived Income Adequacy

We will assess group differences in perceived income adequacy as a binary outcome using mixed-effects logistic regression. Models will be adjusted for baseline perceived income adequacy, and blocking variables (baseline A1C, gender, recruitment location). To improve the precision of effect estimates, models will also be adjusted for age, race/ethnicity, immigrant status, educational attainment, annual household income, home ownership, number of children living in the home, marital status, and diabetes duration. Additionally, all models will include baseline A1C data source (study measured vs administrative health data), and group (FoodRx vs comparison) indicator variables. We will include random intercepts for participants (participant study ID) to account for within-subject correlation due to repeated measures, and for primary care clinics (clinic study ID) to account for clustering of participants within clinics. Missing data for covariates will be addressed using full information maximum likelihood.

We will conduct per-protocol and as-treated sensitivity analyses for perceived income adequacy as described in Section 7.2.

Subjective Social Status

We will assess group differences in subjective social status as a continuous outcome using mixed-effects linear regression. Models will be adjusted for baseline subjective social status, and blocking variables (baseline A1C, gender, recruitment location). To improve the precision of effect estimates, models will also be adjusted for age, race/ethnicity, immigrant status, educational attainment, annual household income, home ownership, number of children living in the home, marital status, and diabetes duration. Additionally, all models will include baseline A1C data source (study measured vs administrative health data), and group (FoodRx vs comparison) indicator variables. We will include random intercepts for participants (participant study ID) to account for within-subject correlation due to repeated measures, and for primary care clinics (clinic study ID) to account for clustering of participants within clinics. Missing data for covariates will be addressed using full information maximum likelihood.

We will conduct per-protocol and as-treated sensitivity analyses for subjective social status as described in Section 7.2.

7.7 Fourth Manuscript

This paper will report results for diabetes-specific PROMs (secondary outcomes) at 12 months, including diabetes self-efficacy, diabetes self-management, diabetes distress, diabetes competing demands, perceived financial barriers to chronic disease care, and hypoglycemic episodes.

Diabetes Self-Efficacy

We will assess group differences in diabetes self-efficacy as a continuous outcome using mixed-effects linear regression. Models will be adjusted for baseline diabetes self-efficacy, and blocking variables (baseline A1C, gender, recruitment location). To improve the precision of effect estimates, models will also be adjusted for age, race/ethnicity, educational attainment, annual household income, years lived in Canada, household composition, marital status, and diabetes duration. Additionally, all models will include baseline A1C data source (study measured vs administrative health data), and group (FoodRx vs comparison) indicator variables. We will include random intercepts for participants (participant study ID) to account for within-subject correlation due to repeated measures, and for primary care clinics (clinic study ID) to account for clustering of participants within clinics. Missing data for covariates will be addressed using full information maximum likelihood.

We will conduct subgroup analyses for diabetes self-efficacy by gender, severity of household food insecurity, recruitment location (urban setting, rural setting, Indigenous primary care clinic), Indigenous identity (self-identified as First Nations, Inuk, Métis), baseline A1C (6.5%-8.5%; 8.6%-12%), and insulin use (yes, any vs no, none).

In addition to per-protocol and as-treated analyses, we will conduct sensitivity analyses for diabetes self-efficacy as described in Section 7.2.

Diabetes Self-Management

We will assess group differences in diabetes self management as a continuous outcome using mixed-effects linear regression. Models will be adjusted for baseline diabetes self management, and blocking variables (baseline A1C, gender, recruitment location). To improve the precision of effect estimates, models will also be adjusted for age, race/ethnicity, educational attainment, annual household income, years lived in Canada, household composition, marital status, and diabetes duration. Additionally, all models will include baseline A1C data source (study measured vs administrative health data), and group (FoodRx vs comparison) indicator variables. We will include random intercepts for participants (participant study ID) to account for within-subject correlation due to repeated measures, and for primary care clinics (clinic study ID) to account for clustering of participants within clinics. Missing data for covariates will be addressed using full information maximum likelihood.

In addition to per-protocol and as-treated analyses, we will conduct sensitivity analyses for diabetes self management as described in Section 7.2.

Diabetes Distress

We will assess group differences in diabetes distress as a continuous outcome using mixed-effects linear regression. Models will be adjusted for baseline diabetes distress, and blocking variables (baseline A1C, gender, recruitment location). To improve the precision of effect estimates, models will also be adjusted for age, race/ethnicity, educational attainment, annual household income, years lived in Canada, household composition, marital status, and diabetes duration. Additionally, all models will include baseline A1C data source (study measured vs administrative health data), and group (FoodRx vs comparison) indicator variables. We will include random intercepts for participants (participant study ID) to account for within-subject correlation due to repeated measures, and for primary care clinics (clinic study ID) to account for clustering of participants within clinics. Missing data for covariates will be addressed using full information maximum likelihood.

In addition to per-protocol and as-treated analyses, we will conduct sensitivity analyses for diabetes distress to examine the impact on results when diabetes distress is modelled as an ordinal outcome using mixed-effects logistic regression.

Diabetes Competing Demands

We will assess group differences in diabetes competing demands as a binary outcome using mixed-effects logistic regression. Models will be adjusted for baseline diabetes competing demands, and blocking variables (baseline A1C, gender, recruitment location). To improve the precision of effect estimates, models will also be adjusted for age, race/ethnicity, educational attainment, annual household income, years lived in Canada, household composition, marital status, and diabetes duration. Additionally, all models will include baseline A1C data source (study measured vs administrative health data), and group (FoodRx vs comparison) indicator variables. We will include random intercepts for participants (participant study ID) to account for within-subject correlation due to repeated measures, and for primary care clinics (clinic study ID) to account for clustering of participants within clinics. Missing data for covariates will be addressed using full information maximum likelihood.

In addition to per-protocol and as-treated analyses, we will conduct sensitivity analyses for diabetes competing demands as described in Section 7.2.

Hypoglycemic Episode Frequency

We will assess group differences in hypoglycemic episode frequency as an ordinal outcome using mixed-effects logistic regression. Models will be adjusted for baseline hypoglycemic episode frequency, and blocking variables (baseline A1C, gender, recruitment location). To improve the precision of effect estimates, models will also be adjusted for age, race/ethnicity, educational attainment, annual household income, years lived in Canada, household composition, marital status, diabetes duration, and physical activity level. Additionally, all models will include baseline A1C data source (study measured vs administrative health data), and group (FoodRx vs comparison) indicator variables. We will include random intercepts for participants (participant study ID) to account for within-subject correlation due to repeated measures, and for primary care clinics (clinic study ID) to account for clustering of participants within clinics. Missing data for covariates will be addressed using full information maximum likelihood.

In addition to per-protocol and as-treated analyses, we will conduct sensitivity analyses for hypoglycemic episode frequency as described in Section 7.2.

7.8 Fifth Manuscript

This paper will report results for healthcare resource use, psychosocial well-being and self-rated health (secondary outcomes), and work productivity (exploratory outcome) at 12-months.

Healthcare Costs

We will assess group differences in healthcare costs using annual total healthcare costs as the outcome using a Generalized Linear Model with a Tweedie distribution and log link, which accounts for skewed distributions by modeling costs using a compound Poisson-Gamma distribution. This approach will effectively handle zero-inflated and highly variable expenditure data. Models will be adjusted for baseline healthcare resource use (i.e. previous years cost), and blocking variables (baseline A1C, gender, recruitment location). To improve the precision of effect estimates, models will also be adjusted for age, race/ethnicity, educational attainment, number of children living in the home, and diabetes duration.

Additionally, all models will include baseline A1C data source (study measured vs administrative health data), and group (FoodRx vs comparison) indicator variables. We will include random intercepts for participants (participant study ID) to account for within-subject correlation due to repeated measures, and for primary care clinics (clinic study ID) to account for clustering of participants within clinics. Missing data for covariates will be addressed using full information maximum likelihood.

We will conduct subgroup analyses for healthcare costs by gender, severity of household food insecurity, recruitment location (urban setting, rural setting, Indigenous primary care clinic), Indigenous identity (self-identified as First Nations, Inuk, Métis), baseline A1C (6.5%-8.5%; 8.6%-12%), and insulin use.

In addition to per-protocol and as-treated analyses, we will conduct sensitivity analyses for healthcare costs to examine the impact of pharmacy costs.

Self-Rated Health

We will assess group differences in EQ-5D-5L index values as a continuous outcome using mixed-effects linear regression. Models will be adjusted for baseline EQ-5D-5L index values, and blocking variables (baseline A1C, gender, recruitment location). To improve the precision of effect estimates, models will also be adjusted for age, race/ethnicity, educational attainment, number of children living in the home, and diabetes duration.

Additionally, all models will include baseline A1C data source (study measured vs administrative health data), and group (FoodRx vs comparison) indicator variables. We will include random intercepts for participants (participant study ID) to account for within-subject correlation due to repeated measures, and for primary care clinics (clinic study ID) to account for clustering of participants within clinics. Missing data for covariates will be addressed using full information maximum likelihood.

In addition to per-protocol and as-treated analyses, we will conduct sensitivity analyses for EQ-5D-5L index values to examine the impact of individual health dimensions on differences in overall utility.

Work Productivity and Activity Impairment

We will assess group differences in Work Productivity and Activity Impairment scores as a continuous outcome using mixed-effects binomial regression. Models will be adjusted for baseline Work Productivity and Impairment scores, and blocking variables (baseline A1C, gender, recruitment location). To improve the precision of effect estimates, models will also be adjusted for age, race/ethnicity, educational attainment, number of children living in the home, and diabetes duration.

Additionally, all models will include baseline A1C data source (study measured vs administrative health data), and group (FoodRx vs comparison) indicator variables. We will include random intercepts for participants (participant study ID) to account for within-subject correlation due to repeated measures, and for primary care clinics (clinic study ID) to account for clustering of participants within clinics. Missing data for covariates will be addressed using full information maximum likelihood.

In addition to per-protocol and as-treated analyses, we will conduct sensitivity analyses for Work Productivity and Impairment scores as described in Section 7.2.

Psychosocial Well-Being

We will assess group differences in WHO Well-Being Index scores as a continuous outcome using mixed-effects linear regression. Models will be adjusted for baseline WHO Well-Being Index scores, and blocking variables (baseline A1C, gender, recruitment location). To improve the precision of effect estimates, models will also be adjusted for age, race/ethnicity, educational attainment, number of children living in the home, and diabetes duration.

Additionally, all models will include baseline A1C data source (study measured vs administrative health data), and group (FoodRx vs comparison) indicator variables. We will include random intercepts for participants (participant study ID) to account for within-subject correlation due to repeated measures, and for primary care clinics (clinic study ID) to account for clustering of participants within clinics. Missing data for covariates will be addressed using full information maximum likelihood.

In addition to per-protocol and as-treated analyses, we will conduct sensitivity analyses for WHO Well-Being Index scores by 1) modeling scores as a binary outcome using validated cut points (≤ 50 for impaired well-being, ≤ 28 for likely depression), and 2) assessing clinically meaningful improvements, defined as a ≥ 10 -point increase on the 0-100 scale^{91, 124} using mixed-effects logistic regression.

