5.3.3 Work Productivity and Activity Impairment

Work productivity and impairment was assessed using the validated 6-item Work Productivity and Impairment tool. The questions measure impairments in paid work and regular activities due to health issues in the past 7 days.^{104, 105} The tool yields 4 percentage scores including absenteeism (work time missed), presenteeism (impairment at work/reduced on-the-job effectiveness), work productivity loss (overall work impairment), and activity Impairment (impairment in non-work activities). Higher scores indicate greater productivity loss and/or activity impairment. Work productivity and activity impairment will be analyzed as a continuous outcome.

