5.3.5 Physical Activity Level

Physical activity level was assessed using a validated single-item physical activity tool, which measures how many days during the past 7 days participants took part in 30 minutes or more of moderate to vigorous exercise.¹⁰⁷ Response values range from 0 (0 days) to 7 (7 days) with higher numbers indicating higher physical activity levels. Physical activity level will be analyzed as a discrete outcome.

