7.9 Sixth Manuscript

This paper will assess for evidence of improvements in trade-offs that might result from reduced food insecurity through the FoodRx intervention. In this paper, we will report results for self-reported medication adherence, physical activity level, and perceived financial barriers to chronic disease care.

Medication Adherence

We will assess group differences in medication adherence as a continuous outcome using mixed-effects linear regression. Models will be adjusted for baseline medication adherence, and blocking variables (baseline A1C, gender, recruitment location). To improve the precision of effect estimates, models will also be adjusted for age, race/ethnicity, educational attainment, annual household income, marital status, number of children living in the home, and diabetes duration.

Additionally, all models will include baseline A1C data source (study measured vs administrative health data), and group (FoodRx vs comparison) indicator variables. We will include random intercepts for participants (participant study ID) to account for within-subject correlation due to repeated measures, and for primary care clinics (clinic study ID) to account for clustering of participants within clinics.

In addition to per-protocol and as-treated analyses, we will conduct sensitivity analyses for medication adherence as described in Section 7.2.

Physical Activity Level

We will assess group differences in physical activity level as a discrete outcome using mixed-effects Poisson regression. Models will be adjusted for baseline physical activity level, and blocking variables (baseline A1C, gender, recruitment location). To improve the precision of effect estimates, models will also be adjusted for age, race/ethnicity, educational attainment, annual household income, marital status, number of children living in the home, BMI, smoking status, and diabetes duration. Additionally, all models will include baseline A1C data source (study measured vs administrative health data), and group (FoodRx vs comparison) indicator variables. We will include random intercepts for participants (participant study ID) to account for within-subject correlation due to repeated measures, and for primary care clinics (clinic study ID) to account for clustering of participants within clinics. Missing data for covariates will be addressed using full information maximum likelihood.

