In addition to per-protocol and as-treated analyses, we will conduct sensitivity analyses for physical activity level to examine the impact on results when physical activity level is modeled as an ordinal outcome using mixed-effects logistic regression.

Perceived Financial Barriers to Chronic Disease Care

We will assess group differences in perceived financial barriers to chronic disease care as a binary outcome using mixed-effects logistic regression. Models will be adjusted for baseline perceived financial barriers to chronic disease care, and blocking variables (baseline A1C, gender, recruitment location). To improve the precision of effect estimates, models will also be adjusted for age, race/ethnicity, educational attainment, annual household income, years lived in Canada, household composition, marital status, and diabetes duration. Additionally, all models will include baseline A1C data source (study measured vs administrative health data), and group (FoodRx vs comparison) indicator variables. We will include random intercepts for participants (participant study ID) to account for within-subject correlation due to repeated measures, and for primary care clinics (clinic study ID) to account for clustering of participants within clinics. Missing data for covariates will be addressed using full information maximum likelihood.

In addition to per-protocol and as-treated analyses, we will conduct sensitivity analyses for perceived financial barriers to chronic disease care as described in Section 7.2.

References

1. Government of Alberta. Health Care System Cost of People With Diabetes 2013 [Available from: <https://open.alberta.ca/dataset/a2a60d91-081e-42c8-8d4a-466bb3506399/resource/34c90d83-caa3-4def-ab78-3a8987e2d7d7/download/phsb-03-2013-diabetes-cost.pdf>].
2. American Diabetes A. Economic Costs of Diabetes in the U.S. in 2017. *Diabetes Care*. 2018;41(5):917-28.
3. Association AD. *Diabetes Care*.
4. Diabetes Canada. New diabetes rates released with urgent plea for governments to implement national diabetes strategy 2019 [Available from: <https://www.diabetes.ca/media-room/press-releases/new-diabetes-rates-released-with-urgent-plea-for-governments-to-implement-national-diabetes-strategy#:~:text=Jan%20Hux%2C%20President%20and%20CEO,under%20%2430%20billion%20this%20year>].

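### Work productivity scores are percentages, but the plan gives them a binomial model with no stated number of trials, so their standard errors can be well off in either direction

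*SAP*

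**What the plan says.** SAP Section 5.3.3 describes the instrument: "The tool yields 4 percentage scores including absenteeism (work time missed), presenteeism (impairment at work/reduced on-the-job effectiveness", with overall work impairment and activity impairment as the other two. It then states: "Work productivity and activity impairment will be analyzed as a continuous outcome".

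Section 7.8 analyses these scores "as a continuous outcome using mixed-effects binomial regression", adjusted for the baseline score, with random intercepts for participant and clinic. It names no number of trials, link, dispersion term or robust variance. Beyond the main model it plans only "sensitivity analyses for Work Productivity and Impairment scores as described in Section 7.2". Section 7.2 contains per-protocol and as-treated analyses, and no alternative error model.

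The SAP treats comparable scores differently. Medication adherence (0-100%, Sections 5.3.4 and 7.9), the WHO well-being score (with a 0-100% form, Sections 5.2.4 and 7.8) and the share of energy from ultra-processed foods (Section 7.5) all get mixed-effects linear regression.

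**The concern.** A binomial model describes successes out of a known number of independent trials, and its variance follows from that number. A percentage impairment score has no such number, so calling it continuous and fitting a binomial model do not go together. An analyst has to choose a coding, and the two obvious choices push the standard error in opposite directions. Section 6.2 puts the weight of interpretation on effect sizes and confidence intervals, so the interval is what readers will use. The choice could also be made after the data are seen.

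**Working it through.** **Inputs**
- Scale and model: Sections 5.3.3 and 7.8, as above.
- Rows per person: unclear. Section 3.3 has collection at 0, 6 and 12 months. Section 7.8 reports at 12 months but keeps a participant intercept for repeated measures. Section 6.5 describes group-by-time contrasts.
- Mean and SD: not given. Assumed mean 30-40%, SD 20-31 points.
- Sample: 594 x 0.70 = 415.8, taken as 416. Fewer people will contribute to the paid-work scores, but the ratios below hardly depend on n.
- The SAP has no planning figure for this outcome to reproduce.

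**Step 1: variance implied by each coding, no random intercept, mean 30%**
- As x out of 100: sqrt(0.3 x 0.7 / 100) = 0.046. Against a true SD of 0.20 to 0.30 this is too small by 0.20/0.046 = 4.4 to 0.30/0.046 = 6.5 times.
- As a 0-1 fraction (one trial): sqrt(0.21) = 0.458. This is too large by 0.458/0.30 = 1.5 to 0.458/0.20 = 2.3 times.

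**Step 2: add the planned participant intercept**

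Scores were simulated under no group effect, with person-level and occasion-level variation (correlation between occasions about 0.5-0.7). The model was fitted by maximum likelihood with adaptive quadrature, 120-200 replicates per setting (300 for the fraction coding with a single row, fitted with a fixed 20-node grid). The clinic intercept and the other covariates were left out.

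| Coding | Rows and contrast | Model SE / true SE | Coverage of 95% CI |
|---|---|---|---|
| 0-1 fraction | 12-month row only, group difference | 1.5-2.2 | 0.997-1.00 |
| 0-1 fraction | 6 and 12 months, group difference at 12 | 1.5-2.2 (1.7-2.7 with baseline score as covariate) | 0.99-1.00 |
| 0-1 fraction | 0, 6 and 12 months, group-by-time change | 2.3-3.5 | 1.00 |
| x out of 100 | 12-month row only, group difference | 0.89-1.07 | 0.93-0.97 |
| x out of 100 | 6 and 12 months, group difference at 12 | 0.82-1.01 | 0.87-0.97 |
| x out of 100 | 0, 6 and 12 months, group-by-time change | 0.19-0.33 | 0.33-0.45 |

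A further simulation of the fraction coding with the intercept gave ratios of 1.4-2.3. A separate single-row simulation of x out of 100 (n = 417, 400 replicates) gave ratios of 0.98-1.05 and type I error of 0.037-0.052, in line with the fourth row of the table.

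**Step 3: why the change contrast fails under x out of 100**

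Within a person the intercept cancels and only binomial noise is left. On the logit scale that is 1/(100 x 0.21) = 0.048 per occasion, so 0.095 for a difference of two occasions. With 208 per arm, the SE is sqrt(0.095 x 2/208) = 0.030. The simulated model SE was 0.032-0.037, against a true 0.10-0.17.

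**Step 4: numerical integration matters**

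A fixed 80-node grid, with 6- and 12-month rows and the group difference at 12 months, gave 0.058/0.184 = 0.32 and 0.056/0.189 = 0.30, with coverage 0.43 and 0.49. That grid is too coarse. With 200 trials per person the likelihood for one intercept has SD of about 1/sqrt(200 x 0.21) = 0.15, while the nodes lie about 0.6 apart when the intercept SD is near 1.7. Adaptive quadrature gives the fifth row of the table instead. The one-third figure therefore belongs to the group-by-time change, or to a fit with coarse integration. It does not belong to an accurately fitted 12-month difference.

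**The case against.** The case against making much of this is a fair one.

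- Under x out of 100 with a single 12-month row, the participant intercept acts as an observation-level effect and the error almost vanishes. This stands, and it also holds approximately for a 12-month difference fitted accurately with two rows. The SAP fixes neither the coding nor the rows, so it cannot rely on this case.
- The fraction coding gives intervals that are too wide, so it produces no false positives. This stands, but the lost precision is large.
- A binomial-family model on a fraction has the same mean model as a fractional logit. True. What is missing is the variance, and that is where the error lies.
- Linear regression also ignores the bounds. True, but it estimates its residual variance from the data, and the SAP already accepts it for similar scores.
- Section 6.1 promises to check every model's assumptions and correct violations. The remedies it names are only for proportional odds, and a check cannot supply a missing number of trials.

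Two stronger readings are tempting, and the documents do not support them. The first is that the intervals are bound to be 4.4 to 6.5 times too narrow; that figure leaves out the planned participant intercept. The second is that active days share the defect, because the SAP models "physical activity level as a discrete outcome using mixed-effects Poisson regression" although "Response values range from 0 (0 days) to 7 (7 days) with higher numbers indicating higher physical activity levels". Poisson does put 5% (mean 4) to 13% (mean 5) of its probability above 7 days. With the planned participant intercept, however, simulated coverage was 0.945-0.975 in most settings. It was clearly off only for under-dispersed weeks (mean 5, SD 1.3), where the interval is too wide (SE 0.044 against 0.024). The SAP also plans a check in which "physical activity level is modeled as an ordinal outcome using mixed-effects logistic regression". Which of two planned models leads is a matter of preference.

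**Conclusion.** The point holds for the work productivity and activity impairment scores. The named model does not suit a percentage score, and the SAP leaves open the choices that decide how wrong the intervals are.

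- **Fraction coding:** standard errors for the 12-month group difference are about 1.4-2.3 times too large, and more for change contrasts or with baseline adjustment.
- **x out of 100, repeated rows:** about one third of the true value or less for the group-by-time change (coverage about 45% or lower). The loss is mild for an accurately fitted 12-month difference.
- **x out of 100, single row:** close to nominal.

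These sizes rest on assumed means, SDs and within-person correlations, and on a model without clinic effects. The outcome is exploratory. The primary A1C analysis and the sample size of 594 are not touched. For active days, at most a note is warranted that Poisson intervals can be too wide if the counts are under-dispersed.

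**What to change.** In Section 7.8, replace the binomial model for the work productivity and activity impairment scores with one of these:

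1. mixed-effects linear regression, as for the SAP's other 0-100 scores; or
2. a fractional logit with robust standard errors clustered by participant.

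In the same sentence, state which visits enter as outcome rows and which contrast is reported at 12 months.

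The cost is a wording change, made before the outcome is analysed. The linear model reports a difference in percentage points and does not respect the bounds. The fractional logit respects them, but clinic clustering would then need its own statement. Active days need no change to the main model, since the planned ordinal analysis already serves as the check.
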